### Subgroup analyses

In alignment with sex and gender equity in research (SAGER) guidelines, we plan to conduct exploratory analyses for each of our effectiveness outcomes for males and females to explore potential sex differences in each of these outcomes. We will include sex and its interaction with time and group by time in the models. We will report the interaction p-value along with forest plots to visualize the subgroup treatment effects, along with 95% confidence intervals.

### Process evaluation analysis

The multi-methods process evaluation analysis will assess how the PT-led primary care model for LBP was implemented, the potential mechanisms of the model, the experiences and perspectives of patients and primary care team members toward the model, and how the context influenced implementation and outcomes. The analysis is guided by and intended to inform refinements to our program theory for the PT-led primary care model program for LBP (**Figure 1**).

We will assess how the PT-led primary care model and usual care model were implemented and how the model influenced healthcare for people with LBP by:

- 1) Describing and comparing the proportion of patient participants who received timely access to LBP care between trial arms. The intended implementation outcome is that patient participants seeking primary care for LBP receive timely access (within 48 hours) to a LBP assessment from a PT in the PT-led primary care model for LBP. Access within 48 hours will be presented as incidence rates with confidence intervals and compared by calculating relative risks with confidence intervals using GEE-type variance estimators to account for clustering, using an exchangeable working correlation matrix. We will use empirical covariance (“sandwich”) bias-adjusted (residual-based) estimators and the Fay and Graubard correction to account for small number of clusters. We will incorporate the same covariates as with our effectiveness analysis.
- 2) Describing the proportion of patient participants in the PT-led primary care arm who saw the PT as the first point of contact for the current episode of LBP.
- 3) Describing and comparing the proportion of patient participants who are categorized as medium or high risk on the STarT Back tool who access PT services between trial arms. The intended implementation outcome is that patient participants with LBP at medium or high risk of ongoing pain and disability access PT services, either through a referral (for participants who have access to PT services) or through additional PT care from the primary care PT (for participants who would not otherwise have access to PT services). We will report the proportion of participants at medium or high risk receiving PT care as incidence rates with confidence intervals and compared by calculating relative risks with confidence intervals using GEE-type variance estimators, accounting for clustering, using an exchangeable working correlation matrix. We will use empirical covariance (“sandwich”) bias-adjusted (residual-based) estimators and the Fay and Graubard correction to account for small number of clusters. We will incorporate the same covariates as with our effectiveness analysis.
- 4) Describing and comparing the LBP management provided between trial arms and comparing the care provided to practice guidelines using recent World Health Organization (WHO) LBP guidelines to assess the alignment of the care provided with practice guideline recommendations. The 10 recommended interventions in the WHO guidelines are: structured education, exercise, needling

therapies, spinal manipulation, massage, operant therapy, cognitive behavioural therapy, non-steroidal anti-inflammatory drugs, topical cayenne pepper, and multicomponent biopsychosocial care. Interventions that are recommended against include: traction, ultrasound, transcutaneous electrical nerve stimulation, and lumbar supports. Additionally, referrals for diagnostic imaging or physician specialist visits for spinal injections or surgery consultations are rarely needed for LBP and thus will be compared between arms for a potential reduction in low-value care. The intended implementation outcome is that patient participants receive care recommended in practice guidelines and do not receive care recommended against in practice guidelines, and that a low proportion of people receive *referrals or prescriptions* for diagnostic imaging, physician specialist, or medications outside of NSAIDs. Receipt of each intervention recommended by the guidelines, recommended against by the guidelines, and referrals (for imaging, spinal injections, or surgical consults) will be presented as incidence rates with confidence intervals and compared by calculating relative risks with confidence intervals using GEE-type robust variance estimates, accounting for clustering, using an exchangeable working correlation matrix. We will use empirical covariance (“sandwich”) bias-adjusted (residual-based) estimators and the Fay and Graubard correction to account for small number of clusters. We will incorporate the same covariates as with our effectiveness analysis.

5) Describing adherence to PT primary care recommendations. The intended implementation outcome is that patient participants report actioning the initial recommendations for physical activity and exercise and that those who were recommended to access PT services report doing so.

To assess potential mechanisms of the PT-led primary care model, if there is a significant treatment effect, we will conduct a series of mediation analyses to assess whether changes in LBP-related disability is explained by changes in self-efficacy (PSEQ) or changes in psychosocial risk factors (PHQ-2, PCS, TSK-11) for persistent LBP-related disability. We will carry out this mediation analysis for each of the self-efficacy and psychosocial risk factor variables in our entire sample and in the subgroup of patient participants identified as high-risk using the STarT Back classification. We hypothesize that change in self-efficacy will mediate the relationship between the intervention arm and RMDQ score in the full patient participant sample and that change in psychosocial risk factors will mediate the relationship between treatment arm and RMDQ score in the high-risk subgroup. We will use a stepwise approach to exploring the temporal trends and dynamics of the treatment effect across repeated measures as proposed by Beril and colleagues, along with our theoretical insights regarding the mediation effect, when considering the appropriate mediation model. The indirect effect, or the intervention effect that can be explained by the mediator, will be determined as the difference between the total effect of the intervention and the direct effect of the intervention. The significance of this effect can be used to statistically evaluate the possibility of mediation. In this context, the total effect is the intervention effect obtained in the full model described in the trial. To be consistent with our primary outcome measure in the trial, we will be concerned with the time-specific mediation on the RMDQ outcome at the 12-month follow-up. These effect measures will allow us to present the proportion of the total effect that is mediated through the respective measures of interest. Development of the causal/associated conceptual model has allowed us to consider, and control for where needed, mediation analysis assumptions; that is, there is no intervention-outcome, mediator-outcome, or intervention-mediator confounding or mediator-outcome confounding that is influenced by the intervention itself. Additionally, as part of exploring potential mechanisms, we will describe the proportion of any differences in total costs that are due to differences in healthcare utilization costs (and if so what healthcare services) and what proportion of any differences in total costs are due to differences in costs due to missed occupational activities.

We will further explore potential mechanisms for intervention effects by conducting a planned subgroup analysis for all process outcomes, RMDQ, and costs based on STarT Back risk classification (low,

medium, or high), recognizing that this analysis is exploratory and likely to be underpowered. We hypothesize that the participants in the PT-led group classified as low risk will: be less likely to receive requisitions for diagnostic imaging, referrals to specialist physicians, and prescriptions for medications; demonstrate reduced costs; and show similar disability outcomes in comparison to patient participants in the usual care group. We hypothesize that participants in the PT-led group classified as medium risk will: be more likely to access PT services; receive LBP management closer aligned with guidelines; receive fewer requisitions for diagnostic imaging, prescriptions for medications, and referrals to specialist physicians; demonstrate reduced costs; and have reduced LBP-related disability. Finally, we hypothesize that participants in the PT-led group classified as high risk will: be more likely to access PT services; receive LBP management closer aligned with guidelines and more targeted care for psychosocial risk factors of persistent LBP-related disability; show greater reductions in the psychosocial risk factors; demonstrate reduced costs; and have reduced LBP-related disability.

To explore the experiences and perspectives of patients, PTs, and other primary care health professionals who have participated in the PT-led primary care model for LBP, qualitative interviews with patient participants, the PTs, and other health professional primary care team members will be recorded, transcribed, and coded independently by two investigators. An inductive qualitative analysis will be completed in an interpretive description tradition. Interpretive description was chosen because of its emphasis on adding an interpretive lens during the analysis process in order identify meaningful themes from the data that can be applied in practice. This qualitative approach is therefore well aligned with our process evaluation goals to understand experiences and perspectives with the PT-led primary care model, potentially leading to refinements in the model of care, the program theory, or plans for scaling the intervention if effective. To promote rigour, we will use: two independent coders for the first two to three transcripts for each group (patient participants, PTs, other health professionals) and meet to reach agreement on the initial coding structure; reflexivity journaling and reflexive dialogue amongst team members throughout the analytic process; field notes and written memos; prolonged engagement within the data; and an audit trail of the research process and analytic decisions.

To explore how the context influenced the implementation of the PT-led primary care model for LBP, a concurrent mixed methods analysis will be conducted using the quantitative data collected to describe how the intervention is being implemented (analysis described above) and qualitative interview data from patient participants, PTs, other primary care health professionals, medical office assistants, and primary care organizational leaders. Qualitative analysis will begin by having multiple research team members immerse themselves in the data. Data will be coded by two independent research team members using an in-depth deductive (codes derived from CFIR constructs) and inductive (codes derived from the data) coding process in alignment with the CFIR User Guide and previous research. Further, we will code relationships between constructs to capture how constructs interact, and how implementation determinants relate to how the model was implemented. Integration of qualitative and quantitative will be achieved through the design (convergent mixed methods), methods (merging), and interpretation (narrative, and joint displays). Merging of qualitative and quantitative data will be achieved by linking participant characteristics, implementation data, and qualitative interview data. By bringing together the quantitative and qualitative data for analysis and linking this data at the level of the patient participant and cluster, we will be able to carry out an in-depth analysis of how context influenced implementation. Integration at the interpretation phase will be achieved using a weaving approach to interpret and report qualitative and quantitative findings together. Joint displays will be used to bring data together in a visual display if appropriate.

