The trial incorporates a multi-methods process evaluation informed by United Kingdom Medical Research Council (MRC) guidance for developing and evaluating complex interventions, the Consolidated Framework for Implementation Research (CFIR), and findings from the process evaluation from our pilot trial. Process evaluations assess how interventions were implemented and under what conditions. They are important to help interpret trial results (e.g., explaining why an intervention fails or has unexpected consequences, or why it works and how it can be refined). Process evaluations can be particularly valuable for informing future implementation and sustainability of complex healthcare interventions. Our process evaluation is informed by and intended to refine our program theory for the PT-led primary care model program for LBP (**Figure 1**). The program theory

describes how the PT-led primary care model for low back pain is intended to lead to improvements in trial outcomes.

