### **Sample Size and Power Calculations:**

We used the methodology of Teerenstra et al. to calculate the required number of clusters based on an ANCOVA analysis for the primary outcome (Roland-Morris Disability Questionnaire [RMDQ]) at 12 months adjusting for baseline. Our target sample was 20 clusters (10 per arm) allowing for 1560 patient participants (78 per practice before attrition). Conservatively accounting for attrition of two clusters (resulting in 18 clusters) and 20% of patients (resulting in 63 patients/cluster), this target would achieve 90% power to detect a minimally important mean difference of 2.5 points (Cohen's  $d=0.4$ ) using a two-sided  $\alpha=0.05$  and assuming a standard deviation (SD) of 5.7 points based on pilot study data, a conservative intracluster correlation coefficient of 0.1, a cluster autocorrelation coefficient (correlation between cluster means at baseline and follow-up) of 0.5, and an individual autocorrelation coefficient (correlation between participant scores at baseline and follow-up) of 0.6 informed by our pilot study. An average rate of 1.5 patient participants per site each week over one year would achieve the recruitment target of 1560 participants, which we anticipated based on our pilot study where we recruited and retained four sites and achieved a recruitment rate of >1.7 participants/site/week. Recruitment of 400 patient participants across 18 clusters (22 participants/cluster) would achieve 80% power.

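### The high-risk mediation analysis depends on an unspecified significant treatment effect, and its total effect is defined only by the trial's full model; tie both to the high-risk sample

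*Combined protocol and SAP*

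**What the plan says.** All of this is in the combined protocol and SAP. Under Process evaluation analysis:

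- **Condition.** "if there is a significant treatment effect, we will conduct a series of mediation analyses". The outcome, time point and sample of that effect are not named. Ethics and Dissemination makes the mechanisms paper depend on the intervention being effective, which supports a trial-level reading.
- **Samples.** Each mediator is analysed "in our entire sample and in the subgroup of patient participants identified as high-risk using the STarT Back classification".
- **Hypotheses.** Self-efficacy is expected to mediate in the full sample. The psychosocial risk factors are expected to mediate in the high-risk subgroup.
- **Estimand.** The indirect effect is total minus direct, for RMDQ at 12 months. For the total effect, "the total effect is the intervention effect obtained in the full model described in the trial". There is no separate definition for the subgroup. The significance of the indirect effect is used to judge mediation, and a proportion mediated is reported.
- **Expected pattern by risk class.** Low-risk patients in the PT-led arm are expected to "show similar disability outcomes in comparison to patient participants in the usual care group", while medium- and high-risk patients are expected to have less disability. This subgroup work is described as exploratory and probably underpowered.

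Trial Design gives, as examples of what process evaluations are for, "explaining why an intervention fails or has unexpected consequences, or why it works and how it can be refined".

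**The concern.** Total minus direct is an indirect effect only when both terms describe the same patients and come from comparable models. In the high-risk analysis the direct effect must come from high-risk patients. If the total comes from everyone, the difference between the two contains the gap between the full-sample and high-risk effects as well as any mediation. The plan's own hypotheses say that this gap is not zero.

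The gate has a related weakness. The psychosocial mechanism is hypothesised in the high-risk subgroup, yet whether it is examined turns on a result that low-risk patients, in whom no disability benefit is expected, would dilute. What is at stake is the mechanism conclusion: mediation in high-risk patients could be understated, or left unexamined.

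**Working it through.** Effects are written as points of RMDQ improvement.

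**Inputs from Sample Size and Power Calculations:** SD 5.7; ICC 0.1; cluster autocorrelation 0.5; individual autocorrelation 0.6; 18 clusters (9 per arm) of 63 after attrition; alpha 0.05, two-sided; difference 2.5 points.

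**Step 1: reproduce the plan's power.** With m = 63 per cluster and k = 9 clusters per arm:

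- Design effect: DE = 1 + 62 × 0.1 = 7.2
- Baseline to follow-up correlation of cluster means: r = (63 × 0.1 × 0.5 + 0.9 × 0.6) / 7.2 = 3.69 / 7.2 = 0.5125
- SE = sqrt[2 × 5.7² × 7.2 × (1 − 0.5125²) / (63 × 9)] = sqrt(0.608) = 0.780
- Power for 2.5 points: Φ(2.5/0.780 − 1.96) = Φ(1.245) = 89% (z), or 85% with a noncentral t on 16 df

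The plan says "this target would achieve 90% power to detect a minimally important mean difference of 2.5 points"; the z version reproduces this.

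**Step 2: full-sample effect implied by the risk-class hypotheses.** The documents give directions only. Assumption: 0 in low risk, 2.5 in medium and high risk, and a low-risk share p of 20% to 45%. Then full-sample effect = 2.5 × (1 − p).

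**Step 3: chance that the gate opens.** Take the gate to be the 12-month full-sample RMDQ comparison, with SE 0.780.

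**Step 4: proportion mediated if the populations are mixed.** Let the true high-risk total be 2.5 and the high-risk direct effect 1.5. The true indirect effect is 1.0, and the true proportion is 1.0/2.5 = 40%. Taken literally, the reported proportion is (full-sample total − 1.5) / full-sample total.

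| Low-risk share (assumed) | Full-sample effect | Gate opens, z | Gate opens, t (16 df) | Reported proportion (truth 40%) |
|---|---|---|---|---|
| 0% (full-sample effect 2.5) | 2.50 | 89% | 85% | 40% |
| 20% | 2.00 | 73% | 67% | 0.50/2.00 = 25% |
| one third | 1.67 | 57% | 52% | 0.17/1.67 = 10% |
| 45% | 1.375 | 42% | 38% | −0.125/1.375 = −9% |

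**Limits.** The last column uses true effects, without sampling error and without selection by the gate. If both rules are applied together, only total-effect estimates above about 1.96 × 0.780 = 1.53 (z) or 2.12 × 0.780 = 1.65 (t) get through. With the direct effect held at 1.5, the reported share at those thresholds would be 0.03/1.53 = 2% or 0.15/1.65 = 9%. The share would therefore still be badly understated near the threshold, but not negative on average inputs. The SE is the design approximation, not that of the covariate-adjusted repeated-measures model.

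**The case against.** The strongest reply is that the plan promises to carry out the mediation analysis in each sample, which can mean repeating the whole procedure. The full model would then be the primary specification without the mediator, refitted in the high-risk patients. That is coherent and gives a valid subtraction. The RMDQ analysis by STarT Back class will produce a high-risk total effect in any case, though the text does not link it to the mediation. This stands: the defect is an ambiguity with one harmful reading. A reader might infer that the proportion mediated is bound to be wrong, but nowhere do the documents say that a full-sample total will be combined with a subgroup direct effect.

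A reader might also infer that the mediation will usually not be run. That is not supported either. The only RMDQ effect size in the plan is a "minimally important mean difference of 2.5 points" for the whole trial, at which the gate opens 85-89% of the time. Lower figures need the assumption that 2.5 points applies to medium- and high-risk patients only. A harsher scenario, in which only high-risk patients benefit, contradicts the plan's own medium-risk hypothesis and should not be used.

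Three further replies have force.

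- The words about explaining failure are a general example of what process evaluations do, not a commitment for the mediation. The implementation, risk-class and qualitative analyses carry no gate, and the mediators are analysed as secondary outcomes regardless.
- A proportion mediated is unstable when the total effect is near zero, so some condition on reporting that ratio is reasonable. It does not justify withholding the indirect effect itself, nor conditioning one sample's analysis on another sample's p-value.
- The total- and direct-effect models might use different records because of missing mediator data. But the mediators and RMDQ are collected at the same visits (Table 1) and no size can be put on a mismatch, so nothing here rests on it.

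**Conclusion.** The point holds as a specification gap in an exploratory analysis. As written, the plan gives no high-risk total effect, names no sample for the gate, and places its psychosocial hypothesis in the subgroup where both matter. Two analysts following the same sentences could report 40% mediated or, at a one-third low-risk share, 10%. The size depends on subgroup effects and risk shares that the documents do not give; the direction follows from the plan's own hypotheses. The primary RMDQ comparison and its power are not affected. It is worth correcting because it is cheap and the plan was published to settle analytic choices in advance.

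**What to change.** Amend the mediation text before analysis starts, using the route under Protocol and Analysis Plan Amendments:

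1. State that, in each sample, total and direct effects are estimated with the same model form in the same patients. For the high-risk analysis, refit the total-effect model in the high-risk subgroup.
2. Do not make the high-risk mediation conditional on full-sample significance. If a gate is kept for the full-sample mediation, name its outcome, time point and sample.
3. Report indirect effects with confidence intervals. Report the proportion mediated only where the total effect in that sample is clearly non-zero, and state the criterion in advance.

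The cost is a few sentences and a few extra model fits. The downside is that some imprecise exploratory indirect effects will be reported, particularly in the high-risk subgroup; they should be labelled as exploratory.

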## **Ethics and Dissemination:**

Ethics approval for this study has been obtained from the Queen's University Health Science and Affiliated Teaching Hospitals Research Ethics Board (HSREB #6027847). Written consent was obtained from all participants willing to participate.

We plan to mobilize the knowledge generated through this cluster randomized trial and process evaluation through a series of peer-reviewed manuscripts, with the following foci: i) effectiveness of the PT-led primary care model for people with LBP (including patient health, and health system and societal outcomes); ii) how the PT-led primary care model for LBP was implemented; iii) potential mechanisms through which the PT-led primary care model for LBP influences patient health and health system outcomes (if the intervention is effective); iv) experiences and perspectives of patients with LBP who participated in the PT-led primary care model; (v) experiences and perspectives of PTs who participated in implementing the PT-led primary care model for people with LBP; vi) experiences and perspectives of other primary care team members who participated in implementing the PT-led primary care model for people with LBP; and (vii) how the context influenced implementation of the PT-led primary care model for people with LBP. We plan to present these results at national and international conferences on primary care, health services, physiotherapy, and back pain. We will create tailored summary reports for each manuscript for each of the following knowledge user groups: patients, health professionals, primary care team leaders, and health system decision makers.

